5.6.4 Loss to follow-up

For subjects whose status is unclear because they fail to appear for study visits without stating an intention to discontinue or withdraw, the investigator should show "due diligence" by documenting in the source documents steps taken to contact the subject, e.g. dates of telephone calls, registered letters, etc. A patient cannot be considered as lost to follow-up until the time point of his/her scheduled end of study visit has passed.

5.6.5 Early study termination by the sponsor

The study can be terminated at any time for any reason by Novartis. Should this be necessary, the patient should be seen as soon as possible and treated for a prematurely withdrawn patient. The investigator may be informed of additional procedures to be followed in order to ensure that adequate consideration is given to the protection of the patient's interests. The investigator will be responsible for informing the Institutional Review Board/Independent Ethics Committee (IRBs/IECs) of the early termination of the trial.

6 Visit schedule and assessments

The study will consist of a screening epoch, a 112-day treatment epoch and a 56-day follow-up epoch after the last treatment.

[Table 6-1](#) lists all of the assessments and indicates with an “x” when the visits are performed. Patients/subjects must be seen for all visits on the designated day, or as close to it as possible. All data obtained for these assessments must be supported in the patients' source documentation. Visit 2 (baseline) and Visit 101 are performed on the same day (Day 1). Patients are required to complete specific ‘baseline assessments (Inclusion/Exclusion criteria) as part of Visit 2 prior to being randomized and moving into the treatment epoch (Visit 101). Missed or rescheduled visits should not lead to automatic discontinuation.

Patients/subjects who prematurely discontinue the study for any reason should be scheduled for a visit as soon as possible, at which time all of the assessments listed for the final visit will be performed. At this final visit, all dispensed investigational product should be reconciled and the adverse event and concomitant medications reconciled on the CRF.

At a minimum, patients will be contacted for safety evaluations during the 30 days following the last administration of study treatment.

The PRO questionnaires should always be completed before any other assessments at a study visit. **The following assessments should be performed prior to dosing for applicable visits:**

- Physical examination
- Vital signs
- Body weight
- Serum specimen for Safety Laboratory
- Serum pregnancy test
- Urine pregnancy test
- Urinalysis
- Sputum specimens (2 separate specimens) for central analysis
- Pre-dose serum specimen for PK sub-study (if applicable)
- Audiology at Visit 2
- Pre-dose spirometry

[REDACTED]

[REDACTED]

[REDACTED]

Table 6-1 Assessment schedule

Visits should occur on the designated day, or as close to it as possible.

Epoch		Screen		Treatment							Follow-up	
Visit	Day	1	2*	101*	102	103	104	105	106 or TD	201	202 or PSD	
		-28 to -7	1	1	8	29	57	85	113	141	169	
Pre-dose sputum specimens (2 separate specimens) for central analysis (microbiology, [REDACTED])				X	X	X	X	X	X	X	X	
Serum specimen for PK tobramycin concentration ^f	0-1 hour post-dose			X	X							
	1-2 hour post-dose			X	X							
Sputum specimen for tobramycin PK concentration ^g	0-1 hour post-dose			X								
	1-2 hour post-dose			X								
	3-4 hour post-dose							X				
	5-6 hour post-dose					X						
Serum specimen for PK sub-study ^h	Pre-dose			X	X							
	0-1 hour post-dose			X	X							
	1-2 hour post-dose			X	X							
	3-4 hour post-dose			X	X							
	5-6 hour post-dose			X	X							
Audiology ⁱ	X ^p	X ^b			X	X	X	X	X ^j	X ^j		
Spirometry ^k	Routine	X								X	X	
	Pre-& 30±15 min post dose			X	X	X	X	X				
QOL-B, [REDACTED] I			X		X	X	X	X	X	X	X	
Inhalation Device Training ^m			S									
Dispense study drug via IRT			S		S	S	S					

Epoch		Screen		Treatment						Follow-up	
Visit	Day	1	2*	101*	102	103	104	105	106 or TD	201	202 or PSD
		-28 to -7	1	1	8	29	57	85	113	141	169
Administer study drug at site ⁿ				X	X	X	X	X	X		
Study drug accountability					S	S	S	S	S		
Review Concomitant medication	X	X		X	X	X	X	X	X	X	X
Patient electronic diary (e-diary)	Issue patient e-diary			S							
	Download and review patient e-diary				S	S	S	S	S		
	Collect patient e-diary								S		
AE/SAE recordings (including pulmonary exacerbations)	X	X	X	X	X	X	X	X	X	X	X
Record Respiratory-related Hospitalizations	X	X		X	X	X	X	X	X	X	X
Review Surgery and Procedures		X	X	X	X	X	X	X	X	X	X
Record Post inhalation events			X	X	X	X	X	X	X		
Complete Study Disposition page (Screening)			X								
Complete Study disposition page (End of Treatment)									X		
Complete Study disposition page (Follow-Up)											X
Conduct QOL-B exit interview (subset of patients) ^o											X

TD = Study treatment discontinuation; PSD = Premature subject/patient discontinuation

X = assessment to be recorded on clinical data base

S = these assessments are source documentation only and will not be entered into the CRF

*Visit 2 (baseline) and Visit 101 are performed on the same day (Day 1). Patients are required to complete specific 'baseline assessments (Inclusion/Exclusion criteria) prior to being randomized and moving into the treatment epoch (Visit 101).

^a The physical exam will be repeated at Visit 2 only if findings at previous visit are abnormal and clinically significant.

^b To be performed prior to dosing.

^d Obtain only for females of child-bearing potential.

^e Pre-dose sputum specimens (2 separate specimens) will be collected from each patient for central analysis (one each for microbiology [REDACTED] [REDACTED]). If a patient is unable to expectorate, one induced sputum specimen will be taken at baseline. For all post-baseline visits, a deep-throat cough swab can be collected from non-sputum producing patients for microbiology.

^f All subjects will have post-dose serum specimens collected during specified time windows. The time interval is measured from the completion of study drug administration. There must be a minimum of one hour difference between consecutive sampling points. Samples may be obtained from a peripheral site by phlebotomy or through a temporary i.v. site, but not through an existing central access or catheter. A patient who discontinues early and is on study medication will be asked to provide an extra serum specimen at the treatment discontinuation visit.

^g All patients will have post-dose sputum specimens collected for PK testing during specified time windows. The time interval is measured from the completion of study drug administration. In patients who are not able to spontaneously produce sputum, one specimen of induced sputum post-dose per specified interval will be collected. No induced sputum sample for PK will be collected at baseline in patients who had induced sputum pre-dose for microbiology assessments. A patient who discontinues early and is on study medication will be asked to provide an extra sputum specimen at the treatment discontinuation visit.

^h Subjects in the serum PK sub-study will have a pre-dose serum specimen collected prior to administration of study drug. A patient who discontinues early and is on study medication will be asked to provide a pre-dose serum specimen at the treatment discontinuation visit.

ⁱ Audiological assessments will be conducted at selected study sites or in patients with oto-toxic events. Auditory acuity will be measured at frequencies from 250 to 8000Hz using a standard dual-channel audiometer. Audiology can be performed within 3 days of the assigned visit.

^j If audiology is normal up to and including the end of the treatment epoch (Visit 106), audiological examination is not needed at Visits 201 and 202.

^k Spirometric measurements shall be conducted at approximately the same time of day to minimize effects of diurnal variability in lung function.

^l PROs to be completed for whom a validated version in a language well understood by the patient is available. [REDACTED]

1. QOL-B, [REDACTED]

^m Identical training regardless of treatment arm.

ⁿ The ISC will assist subjects in conducting the first study drug inhalation (Visit 101), while the inhalation of the study drug at Visits 102, 103, 104, 105 and 106 (last study drug inhalation) at the study site is performed by the subject in the presence of the ISC.

^o If a patient prematurely discontinues study drug, study drug administration in the presence of the ISC, study drug accountability, post-dose spirometry and post-inhalation events should be assessed at the TD visit provided the patient agrees to inhale study medication during the visit.

^o Exit interviews should be conducted by telephone at the last follow-up visit after completion of the PRO questionnaires and preferably prior to other assessments. Approximately 25 patients are planned to be recruited.

^p Patients with a past history of clinically significant hearing loss in the opinion of the investigator and patients with primary ciliary dyskinesia (PCD) may be eligible only if their hearing threshold at screening audiometry is 25dB or lower at frequencies 0.5-4 kHz.

6.1 Information to be collected on screening failures

All patients/subjects who have signed informed consent but not entered into the next epoch will have the study completion page for the screening epoch, demographics, inclusion/exclusion, and serious adverse event (SAE) data collected. Adverse events that are not SAEs will be followed by the investigator and collected only in the source data.

6.2 Patient demographics/other baseline characteristics

Patient demographic and baseline characteristic data to be collected on all patients include: date of birth, age, sex, race, ethnicity, and source of patient referral. Relevant medical history or current medical condition data include data present before signing informed consent. Where possible, diagnoses and not symptoms will be recorded. History of pulmonary exacerbations will be collected on a specific medical history CRF.

A standard 12 lead ECG will be performed at screening (Visit 1). For eligibility in the study the interpretation of the tracing must be made by a qualified physician and documented. The original ECGs, appropriately signed, should be collected and archived at the study site.

ECGs must be recorded after 10 minutes rest in the supine position to ensure a stable baseline. The preferred sequence of cardiovascular data collection is ECG collection first, followed by vital signs, blood sampling, and spirometry. The Fridericia QT correction formula (QTcF) should be used for clinical decisions.

Each ECG tracing should be labeled with study number, subject initials, subject number, date and time, and filed in the study site source documents. For any ECGs with subject safety concerns, two additional ECGs should be performed to confirm the safety finding. If the ECG findings are clinically relevant and would prevent the patient from participating in the study (taking into account the overall status of the patient as well as the medication profile), the patient should be recorded as a screen failure, should NOT be randomized and should not receive treatment.

Clinically significant abnormalities should be recorded on the relevant section of the medical history/Current medical conditions/AE CRF page as appropriate.

Investigators will have the discretion to record abnormal test findings on the medical history CRF whenever in their judgment, the test abnormality occurred prior to the informed consent signature.

Conditions associated with bronchiectasis disease and signs or symptoms including etiology and age at diagnostic will be captured by using a specific BE-related Medical History CRF page.

Baseline data (using a specific CRF as necessary) such as spirometry, previous hospital admissions and exacerbations, baseline Medical Research Council (MRC) breathlessness score, colonization with *P. aeruginosa* and other organisms, and radiological changes will be collected for calculation of the Bronchiectasis Severity Index (BSI) for all patients. The BSI will serve as a disease-specific severity assessment tool ([Chalmers et al 2014](#)).

Previous medication to be listed includes information for all antibiotics and macrolides administered within the last 12 months prior to Visit 1.

A sputum sample is required to be collected at Visit 1, cultured locally at the site and tested for the presence of *P. aeruginosa*, to ensure patients meet the inclusion criteria.

6.2.1 Chest CT-scan

For each patient all reconstructed series from the most recent available digital computed tomography (CT) chest scan images will be sent to the Central Reader for advanced centralized image analysis. Before sending CT images to the Central Reader by secure file transfer protocol (SFTP) server, courier or eRoom, all images will be de-identified. For each patient CT images will be scored for the presence or absence of BE. Furthermore, all CT images will be scored using the Bauman and Hartmann scoring systems to quantify the presence and extend of key lung disease features including BE, airway wall thickening, trapped air, parenchymal abnormalities and nodules. In addition for a subset of random selected CT images, advanced image analysis of the most appropriate series for each CT scan will be executed in random order to develop the PRAGMA-BE scoring system.

For the development of the Airway Artery (AA) method for objective measurement of airway dimensions CT images from a subset of approximately 30 patients will be used. The following structures will be manually measured: airway lumen area (A_{inner}), airway outer area (A_{outer}) and the area of the accompanying vessel (A) for all visible airway vessel pairs (100-300 per scan) (de Jong et al 2005). From these measurements the following ratios will be computed: A_{outer}/A ; A_{inner}/A ; Airway wall Area (AWA)/A. The automated airway and artery extraction algorithm as developed by the central reader imaging group will subsequently be tuned to match these manual annotations. Automated measurement will be further validated by determining agreement with the same measures derived from manual annotation in this patient cohort. Furthermore, the manual and automated AA-method will be compared to BE and airway wall thickness sub-scores [REDACTED] and spirometry outcomes.

Through image analysis quantitative image analysis parameters will be allocated for each patient to CT images that will be included into the clinical database. The annotated images will be stored within the secured hospital environment on the data storage facility of the Central Reader.

Results from the Phase II study will be used to select the best image analysis strategy to phenotype BE CT images and to fine-tune the automated AA method to be used [REDACTED].

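### As Protocol 6.2.1 reads, the automated airway-artery CT method is tuned and validated on the same roughly 30 manually annotated patients, so the reported agreement would be a training-set figure with upward bias of unknown size

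*Protocol*

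**What the plan says.** Protocol 6.2.1 (Chest CT-scan) sets out the airway-artery work in this order.

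- Sample: "CT images from a subset of approximately 30 patients will be used".
- Manual reference: lumen, outer-airway and vessel areas are measured by hand "for all visible airway vessel pairs (100-300 per scan"), and ratios are formed from them.
- Tuning: the automated extraction algorithm "will subsequently be tuned to match these manual annotations".
- Validation: "Automated measurement will be further validated by determining agreement with the same measures derived from manual annotation in this patient cohort".
- Further comparison: "the manual and automated AA-method will be compared to BE and airway wall thickness sub-scores" (the text that follows is partly redacted) and to spirometry.
- Use: "Results from the Phase II study will be used to select the best image analysis strategy to phenotype BE CT images". The same sentence adds fine-tuning of the automated method; its end is redacted.

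The visible text describes manual airway-artery measurement in no other patients. It mentions no division into tuning and validation patients, no cross-validation and no second annotated set. The visible SAP does not describe this analysis.

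**The concern.** The tuning and validation sentences follow one another and point to the same small set of patients. An algorithm adjusted to reproduce a set of manual readings will agree with those readings better than with readings from new patients. Agreement computed in the tuning patients is apparent agreement, and its expected bias is upward.

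The large number of airway-vessel pairs looks reassuring, but pairs from one scan share patient, scanner and reconstruction. The scans are each patient's latest existing CT, and 6.2.1 states no common acquisition protocol. To the extent that errors are shared within a scan, the effective sample for tuning is closer to 30 than to several thousand.

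At stake is how well the tuned method is believed to measure airways in patients it has not seen. Section 6.2.1 intends the Phase II imaging results to guide later choices, so an optimistic figure could carry forward.

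**Working it through.** The plan gives no agreement statistic, target or sample-size argument for this work, so there is no figure to reproduce. The check is a reading of 6.2.1 followed by an illustration of how large the bias could be.

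**Reading.** Agreement with manual measurement can be computed only where manual measurements exist, and the visible text describes them only in the subset of about 30. The tuning sentence refers to those annotations. The validation sentence refers to the same quantities in this patient cohort. Unless some of the 30 are set aside, which is not stated, the two sets coincide. The visible redactions in 6.2.1 fall after the word sub-scores and at the end of the last sentence, not inside the tuning or validation sentences.

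**Illustration 1: width of the limits of agreement.** Inputs: n = 30 patients (6.2.1). Assumptions not in the documents: p freely tuned parameters, linear tuning, error dominated by patient or scan effects, residual variance 1.

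- Expected mean squared error in the tuning patients: 1 − p/n
- Expected mean squared error in new patients: 1 + p/(n − p − 1)
- Relative width of the limits of agreement: square root of the ratio

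| p | Tuning patients | New patients | Ratio | Square root | Too narrow by about |
|---|---|---|---|---|---|
| 1 | 29/30 = 0.967 | 1 + 1/28 = 1.036 | 0.93 | 0.97 | 3% |
| 3 | 27/30 = 0.900 | 1 + 3/26 = 1.115 | 0.81 | 0.90 | 10% |
| 5 | 25/30 = 0.833 | 1 + 5/24 = 1.208 | 0.69 | 0.83 | 17% |
| 10 | 20/30 = 0.667 | 1 + 10/19 = 1.526 | 0.44 | 0.66 | 34% |

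A simulation for p = 3, 5 and 10 (4,000 replicates) gave ratios of 0.80, 0.69 and 0.44, in line with the formulas.

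**The opposite extreme.** If pairs within a scan were fully independent, n would be 30 × 100 = 3,000 to 30 × 300 = 9,000. With n = 3,000 and p = 10 the ratio is (1 − 10/3000)/(1 + 10/2989) = 0.9967/1.0033 = 0.993, and its square root is 0.997: limits about 0.3% too narrow. The truth lies between the two extremes and depends on a within-scan correlation that the documents do not give.

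**Illustration 2: a different measure.** A simulation of Lin's concordance (2,000 replicates, 30 patients, k tuned patient-level parameters, assumed true explained variance R²) gave:

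| R² | k | Tuning patients | New patients | Difference | Leave-one-patient-out |
|---|---|---|---|---|---|
| 0.95 | 1 | 0.973 | 0.972 | 0.001 | 0.969 |
| 0.95 | 10 | 0.982 | 0.960 | 0.022 | 0.954 |
| 0.80 | 1 | 0.885 | 0.881 | 0.004 | 0.868 |
| 0.80 | 10 | 0.925 | 0.832 | 0.093 | 0.811 |
| 0.60 | 1 | 0.742 | 0.733 | 0.009 | 0.704 |
| 0.60 | 10 | 0.837 | 0.649 | 0.188 | 0.609 |

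The direction is upward in every scenario. The size runs from negligible to about 0.19. Leave-one-patient-out removes the optimism and errs slightly low, by 0.003 to 0.040 in these rows.

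**The case against.** The strongest reply has four parts.

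*Silence is not a statement.* Section 6.2.1 is one paragraph of method description. It does not say that every annotated scan is used for tuning, and the validation sentence refers to the same measures, meaning the same quantities, not the same annotations. A reader might infer that the plan rules out a hold-out; it does not. What stands is that none is specified and that following the text as written leads to training-set agreement. Reading the cohort as the whole trial does not help, because no manual annotation outside the subset is described.

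*The selection criterion is not named.* A reader might infer that the agreement statistic decides which imaging strategy is taken forward. The documents do not support that. They refer to Phase II results in general, which also include the Bauman and Hartmann scores, PRAGMA-BE development, and comparison with CT sub-scores and spirometry. The algorithm is not described as tuned to any of those. This objection stands: agreement may inform the choice, and no more can be said. The other comparisons do not replace held-out agreement, however, since they test association with different measures.

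*The size is assumed.* This also stands. The algorithm is an existing extraction method adjusted to many pairs per scan, not a regression on 30 patient values, and the number of tuned parameters is not given. A range that began at 3 parameters would leave out the low end.

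*This is a development stage, and part of the text is redacted.* Further tuning is foreseen, and later validation may be described in text that cannot be seen or in a separate imaging plan. Redacted content cannot be counted as missing. If such a plan holds patients out, a cross-reference settles the matter.

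**Conclusion.** The point holds in a limited form. As written, 6.2.1 leads to an agreement figure obtained in the patients used for tuning, and its expected bias is upward. That rests on the natural reading that this patient cohort means the annotated subset, and on the absence of any stated patient-level separation.

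The size is not derivable from the documents. Under the linear patient-level model with n = 30, limits of agreement are about 3% to 34% too narrow for 1 to 10 tuned parameters; with independent pairs the effect is near zero.

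A reader might go further and infer that the imaging strategy will be wrongly chosen or that the trial's conclusions are weakened. Neither follows. No selection criterion is named. The airway-artery work is absent from the visible objectives, the visible protocol Section 9 and the visible SAP, and eligibility rests on the investigator's CT assessment. The CFU endpoint, type I error, power and dose selection do not depend on it. This is a cheap improvement to exploratory imaging development.

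**What to change.** Add to Protocol 6.2.1, or to an imaging plan that it cites, that agreement between automated and manual measurement is reported only on patients not used for tuning and that this held-out figure is the validation result. Separate by patient, not by airway pair. Either of these would do:

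- patient-level cross-validation, re-tuning in each fold where that is feasible for this algorithm, which uses all of the roughly 30 patients; or
- a split into tuning and validation patients, fixed before tuning starts.

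If agreement is used when strategies are compared, use the held-out figure.

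The cost is the added wording and, with cross-validation, repeated tuning runs. No further scans, readers or manual measurements are needed. The reported agreement will be somewhat less favourable, and with a fixed split also less precise, because fewer patients contribute to it.

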6.3 Treatment exposure and compliance

Assessment of compliance will be based on the electronic patient diary to capture the number of inhaled capsules in every morning and evening if applicable, and the number of unused capsules returned per patient assessed by the ISC. The ISC will then inform the investigator and/or study personnel who will then record the data in the CRF accordingly.

